Appendix III PATIENT CLINICAL TRIAL WALLET CARD
Appendix IV Actionable Mutations for Sub-Protocol EAY131-E
Appendix V Actions Required in Cases of Increases in Liver Biochemistry and
Evaluation of Hy's Law

TREATMENT SUBPROTOCOL CHAIR

[name] Massachusetts General Hospital [name] [contact] [contact] Email: [contact]

TREATMENT SUBPROTOCOL CO-CHAIR

[name] Memorial Sloan Kettering Cancer Center [name] [contact] [contact] Email: [contact]

TRANSLATIONAL CHAIR

[name] MD PhD Vanderbilt-Ingram Cancer Center [name] [contact] [contact] Email: [contact]

Schema

Cycle = 28 days Accrual Goal: 35

1. Introduction

1.1 Osimertinib (AZ9291)

Osimertinib (AZD9291) is an irreversible, mutant specific EGFR tyrosine kinase inhibitor. It is effective in pre-clinical tumor models and clinical trials in patients with TKI sensitizing and T790M resistant tumors. It is generally well tolerated and its most common side effects are mild rash and diarrhea.

1.2 Supporting Preliminary Data

Activating mutations within the epidermal growth factor receptor (EGFR) mutations are present in approximately 20% of all lung adenocarcinomas. EGFR-mutant cancers are dependent on EGFR signaling for growth and survival, making inhibition of EGFR an attractive therapeutic target. EGFR tyrosine kinase inhibitors (TKIs) including erlotinib and afatinib are FDA approved for the treatment of EGFR-mutant lung cancers based on superior responses and progression free survival compared to cytotoxic chemotherapy.^{1,2} All patients that are treated with EGFR TKIs will eventually develop therapeutic resistance, on average after 10-12 months of therapy.^{1,2}Tumor cells from more than half of patients with such "acquired resistance" contain a recurrent second-site mutation (T790M) in the EGFR kinase domain.^{3,4} EGFR T790M is often described as a gatekeeper mutation, and this substitution results in steric hindrance that prevents drug binding and also changes the receptor affinity for ATP.⁵ At present, there are no FDA approved therapies for patients with EGFR mutant lung cancer who develop acquired resistance mediated by the T790M mutation.

The first- and second- generation EGFR TKIs (erlotinib and afatinib, respectively) were designed to inhibit wild-type EGFR. Recently, a new class of pyrimidinebased EGFR TKIs has been developed which irreversibly inhibits classically sensitizing (EGFR L858R, EGFR exon 19 deletions [ex19del]) and resistant (EGFR T790M) forms of EGFR. The first drug in this class was WZ4002, and additional drugs include osimertinib (AZD9291), CO-1686, HM61713, EGF816 and ASP8273. Osimertinib (AZD9291) has a greater than 200 times selectivity for EGFR L858R/T790M over wild-type EGFR (IC50s 480 nM to 1.8 µM across different cell lines).⁶ Treatment with osimertinib (AZD9291) in EGFR L858R, EGFR ex19del, EGFR L858R/T790M and EGFR ex19del/T790M xenograft tumors also led to profound tumor growth regression. Osimertinib (AZD9291) Investigator's Brochure 2014)

The phase 1 study of osimertinib (AZD9291) (NCT01802632) has shown extremely promising activity, specifically in patients with lung adenocarcinomas that harbor EGFR T790M.⁷ A total of 127 patients with centrally confirmed EGFR T790M who could be evaluated for response: the response rate was 61% (95% CI 52-70) and median PFS was 9.6 months (95% CI, 8.3 to not reached). Among all patients treated, no dose-limiting toxicities were seen at any of the doses evaluated. The most common (>10%) adverse events were diarrhea, rash/acne, nausea, decreased appetite, dry skin, pruritis, fatigue, paronychia, constipation, cough stomatitis, vomiting, anemia, dyspnea, upper respiratory tract infection, headache as presented in the Janne et al 2015 paper. Please refer to the Investigator's Brochure for comprehensive safety data. Rev.2/16

As of 9th February 2015, there were 25 (2.5%) ILD-like events reported out of more than 993 patients exposed to osimertinib (AZD9291). Of these, 12 were CTCAE Grade 1-2 events, 8 were Grade 3-4 events and 3 fatal (Grade 5) events (0.3%) as outlined above. Two events haven't had a CTCAE grade reported yet. 11 patients experienced prolongation of the corrected QT (QTc) interval; none of these 11 events resulted in reduction or discontinuation of osimertinib (AZD9291). There were 7 fatal adverse events; 1/7 of these events was a pneumonia which was reported as being possibly drug-related.

The excellent responses of EGFR T790M harboring lung adenocarcinomas to osimertinib (AZD9291) provide the rationale to assess osimertinib (AZD9291) in other tumors with EGFR T790M. Osimertinib (AZD9291) is also active in preclinical studies against other types of EGFR mutations which suggest that the compound may provide clinical benefit in tumors with other rare EGFR mutations as well.

Comprehensive mutation profiling allows us to identify rare, potentially actionable mutations in a wide array of cancer types. Figure 1 illustrates the frequency of EGFR mutations in various tumor types demonstrating that a broad array of cancers have a low frequency of these mutations of interest. EGFR T790M and other rare variants such as vIII, G719S, L861Q, exon 19 and 20 insertions represent a small minority of these EGFR mutations. In the COSMIC database, we identified listings of EGFR T790M mutations in cancers of the upper aerodigestive tract, the biliary tract, the large intestine, the central nervous system and the skin and we suspect these mutations will be more likely to be commonly identified as comprehensive molecular testing becomes routine for all tumors.

The phase 1 study of osimertinib (AZD9291) was conducted in patients with predominantly EGFR L858R or EGFR ex19del and concurrent EGFR T790M; there is no available clinical data to indicate whether osimertinib (AZD9291) has activity against tumors with other rare EGFR mutations or with T790M alone. There is preclinical data that demonstrates activity of osimertinib (AZD9291) in cells transfected with EGFR G719S, L861Q, exon 19 insertions, EGFR variant III, and HER2 exon 20 insertions.⁶ We propose studying AZD9291 in patients with EGFR T790M in cancers other than lung adenocarcinomas. We also propose assessing the activity of AZD9291 in cancers with rare EGFR mutations among which osimertinib (AZD9291) was efficacious in pre-clinical studies (providing MATCH Level 3 evidence – see MATCH Master Protocol).

Figure 1

Figure 1: Frequency of EGFR mutations in tumor types derived from the cBIO portal (http://www.cbioportal.org/public-portal/). The X-axis denotes the tumor type and the genomic study from which the data was derived. The Y-axis represents the frequency of the EGFR alterations in the studies represented on the X-axis.

Rev. Add29 2. Selection of Patients

Each of the criteria in the checklist that follows must be met, along with the eligibility in the MATCH Master Protocol, in order for a patient to be considered eligible for this study. Use the checklist to confirm a patient's eligibility. For each patient, this checklist must be photocopied, completed and maintained in the patient's chart.

In calculating days of tests and measurements, the day a test or measurement is done is considered Day 0. Therefore, if a test is done on a Monday, the Monday four weeks later would be considered Day 28.

ECOG-ACRIN Patient No.

Patient's Initials (L, F, M)

Physician Signature and Date

- **NOTE:** Policy does not allow for the issuance of waivers to any protocol specified criteria (http://ctep.cancer.gov/protocolDevelopment/policies_deviations.htm). Therefore, all eligibility criteria listed in Section 2 must be met, without exception. The registration of individuals who do not meet all criteria listed in Section 2 can result in the participant being censored from the analysis of the study, and the citation of a major protocol violation during an audit. All questions regarding clarification of eligibility criteria must be directed to the Group's Executive Officer ([contact]) or the Group's Regulatory Officer ([contact]).
- **NOTE:** Institutions may use the eligibility checklist as source documentation if it has been reviewed, signed, and dated prior to registration/randomization by the treating physician.
- **NOTE:** All patients must have signed the relevant treatment consent form.
- Rev. Add29 2.1 Eligibility Criteria
 - _____2.1.1 Patient must fulfill all eligibility criteria outlined in Section 3.1 of MATCH Master Protocol (excluding Section 3.1.6) at the time of registration to treatment step (Step 1, 3, 5, 7).
- Rev. Add13 _____2.1.2 Patients must have either of the below, or another aberration, as determined via the MATCH Master Protocol and according to Appendix IV:
- Rev.2/16 Rev. Add25 Rev. Add29

Rev.2/16

2.1.2.1 Any malignancy except NSCLC withEGFR T790M identified in their tumor, with or without an activating mutation

OR

2.1.2.2 Any malignancy harboring any of the following mutations: EGFR G719A, G719C, G719D, G719S EGFR L861Q, S786I or an EGFR exon 19 in frame insertion mutation.

See Appendix IV for information on the targeted mutations and corresponding Levels of Evidence.

	ECOG-ACRIN Cancer Research Group		EAY131-E Version Date: July 16, 2021 NCI Update Date: August 12, 2015
Rev. Add13	2.1.3	Patients must have an electrocardic to treatment assignment and must l abnormalities in rhythm, conduction e.g. complete left bundle branch blo second-degree heart block.	ogram (ECG) within 8 weeks prior have no clinically important n or morphology of resting ECG ock, third degree heart block, and
		Date of ECG:	
Rev. 2/16	2.1.4	Patients must have an ECHO or a r Pass) within 4 weeks prior to registr ventricular ejection fraction (LVEF) (LLN). If the LLN is not defined at a the patient to be eligible.	nuclear study (MUGA or First ration and must not have a left < institutional lower limit of normal site, the LVEF must be > 50% for
		Date of ECHO/Nuclear Study:	
Rev. Add13	2.1.5	Patients must not have known hype (AZD9291) or compounds of similar or any of the inactive excipients of t	ersensitivity to osimertinib r chemical or biologic composition the tablets.
	2.1.6	Patient must not have received osir 1686, HM61713, EGF816 or ASP82	mertinib (AZD9291), WZ4002, CO- 273 previously.
	2.1.7	Patients known to harbor germline excluded from the study. Prospectivnot required.	EGFR T790M mutations are ve testing for germline mutations is
Rev. Add13	2.1.8	Patients must not have a history of pulmonary fibrosis, organizing pneu obliterans), drug-induced pneumon radiation pneumonitis requiring ster pneumonitis on screening chest con History of radiation pneumonitis in t permitted.	interstitial lung disease, idiopathic umonia (eg, bronchiolitis itis, idiopathic pneumonitis, roids, or evidence of active mputerized tomography (CT) scan. the radiation field (fibrosis) is
Rev. Add13	2.1.9	Patients must not currently be receip CYP3A4 inducters or medications " as defined in Appendix II . Drugs that interval, as defined in Appendix II , a been stable on therapy for the perior medication.	iving treatment with potent known to prolong" the QT interval at "may possibly prolong" the QT are permitted if the patient has od indicated for the specific
Rev. Add13	2.1.10	Patients must agree to not donate s treatment until at least 4 months aft treatment.	sperm from the start of protocol ter the last dose of protocol
		Physician Signature	Date

OPTIONAL: This signature line is provided for use by institutions wishing to use the eligibility checklist as source documentation.

Rev. Add29 3. Osimertinib (AZD9291) Treatment Plan

3.1 Administration Schedule

Osimertinib (AZD9291) is given orally. The dose will be 80mg orally once daily continuously. A cycle is defined as 28 days.

Patients should be instructed that if they vomit after taking a dose, then they must not "make it up" with an extra dose, but instead, resume subsequent doses as prescribed. Any missed dose should be skipped and dosing resumed with subsequent doses.

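### Does the NSCLC exception, stated only in 2.1.2.1, leave it unsettled whether NSCLC with T790M plus a listed rare EGFR mutation may enter?

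*Protocol*

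**What the plan says.** Section 2.1.2 sets the molecular entry requirement: "Patients must have either of the below, or another aberration, as determined via the MATCH Master Protocol" and Appendix IV. Two named routes follow, joined by OR.

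- Section 2.1.2.1, the T790M route: "Any malignancy except NSCLC withEGFR T790M identified in their tumor, with or without an activating mutation".
- Section 2.1.2.2, the rare-mutation route: "Any malignancy harboring any of the following mutations", followed by the G719 variants, L861Q, a codon 786 variant and exon 19 in-frame insertions. It mentions neither NSCLC nor T790M.

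The third route, another aberration under Appendix IV, also carries no tumour-type limit in this document.

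Section 1.2 gives the reasons. It describes the existing clinical experience: "The phase 1 study of osimertinib (AZD9291) was conducted in patients with predominantly EGFR L858R or EGFR ex19del and concurrent EGFR T790M". It adds that "there is no available clinical data to indicate whether osimertinib (AZD9291) has activity against tumors with other rare EGFR mutations or with T790M alone". It then states two aims separately: T790M in cancers other than lung adenocarcinoma, and rare EGFR mutations with preclinical support, the latter without a lung exception.

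The notes that open Section 2 forbid waivers and warn: "The registration of individuals who do not meet all criteria listed in Section 2 can result in the participant being censored from the analysis".

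**The concern.** The exception for NSCLC sits inside one of several alternative routes. A lung tumour carrying both T790M and a listed rare mutation is turned away by one route and admitted by the next, and no sentence says that this was meant.

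The genotype is foreseeable. Section 1.2 reports that, in more than half of lung cancer patients with acquired resistance to EGFR inhibitors, tumour cells "contain a recurrent second-site mutation (T790M) in the EGFR kinase domain". Section 2.1.6 bars osimertinib and five named agents but not erlotinib or afatinib. Section 2.1.7 covers known germline T790M only.

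Two things would be at stake. First, osimertinib is already known to work in T790M-positive lung adenocarcinoma, so responses in tumours with both alterations might lift a result that is meant to inform on rare mutations. Second, if the criterion could be read two ways, the censoring note might allow such a patient to be kept or dropped once the response was known.

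**Working it through.** **1. Entry logic.** Let N = NSCLC, T = T790M present, R = mutation listed in 2.1.2.2. As written, eligible = (not N and T) or R. With the exception carried into 2.1.2.2, eligible = (not N and T) or (R and not (N and T)).

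| N | T | R | 2.1.2.1 | 2.1.2.2 | As written | Exception carried over |
|---|---|---|---|---|---|---|
| no | no | no | no | no | no | no |
| no | no | yes | no | yes | yes | yes |
| no | yes | no | yes | no | yes | yes |
| no | yes | yes | yes | yes | yes | yes |
| yes | no | no | no | no | no | no |
| yes | no | yes | no | yes | yes | yes |
| yes | yes | no | no | no | no | no |
| yes | yes | yes | no | yes | **yes** | **no** |

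Every row has one answer as written. Carrying the exception over would change one of the eight. The Appendix IV route behaves the same way: V774M plus T790M in NSCLC is not stopped by the exception.

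**2. Fit with the aims.** The phase 1 population was mainly L858R or exon 19 deletion with T790M. An NSCLC with G719S plus T790M lies outside that predominant group. The rare-mutation aim has no lung exception. Admitting this tumour under 2.1.2.2 therefore does not contradict Section 1.2.

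**3. The censoring note.** It applies to patients who do not meet every criterion in Section 2. The patient in the last row meets 2.1.2 through 2.1.2.2, so the note does not reach that patient on this ground. The same notes send eligibility questions to Group officers and, where the checklist serves as source documentation, require it to be reviewed, signed and dated before registration. Nothing here places the eligibility decision after response.

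**4. Possible size.** Inputs from the protocol: accrual goal n = 35 (Schema) and a response rate of 61% (95% CI 52 to 70) in 127 evaluable T790M-positive patients (Section 1.2). Assumed, because the document gives none of them: the background rate p0, the response rate r in tumours with both alterations, their number k, and pooling of all patients.

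Expected rate = [p0 × (n − k) + r × k] / n, so the shift per patient = (r − p0) / n.

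- n = 35, p0 = 10%: r = 10% gives 0; r = 30% gives 0.20/35 = 0.57 points; r = 61% gives 0.51/35 = 1.46 points.
- The same at the limits of the phase 1 interval: r = 52% gives 0.42/35 = 1.20 points; r = 70% gives 0.60/35 = 1.71 points.
- n = 35, r = 61%: p0 = 5% gives 0.56/35 = 1.60 points; p0 = 20% gives 0.41/35 = 1.17 points.
- k = 1, 2, 3 with p0 = 10%: expected rates of 11.5%, 12.9%, 14.4% at r = 61%, and 10.6%, 11.1%, 11.7% at r = 30%.
- Assumed rare-mutation subgroup of 20, p0 = 10%: 0.20/20 = 1.0 point at r = 30%; 0.51/20 = 2.55 points at r = 61%.

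The sign depends on r − p0, and r is not known for this genotype. The protocol shown defines no separate rare-mutation analysis, so the subgroup of 20 is hypothetical.

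**The case for a change.** The strongest argument for a change is that 2.1.2.1 is not silent on compound tumours. It describes the T790M route whether or not an activating mutation is also present, and it leaves NSCLC out. One route thus withholds entry from NSCLC with T790M and a second EGFR mutation, while the other grants it when the second mutation is on the list. Section 1.2 never says where a lung tumour with both belongs. One sentence would settle it, and the population would then be fixed beyond dispute before any response is seen.

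Part of this stands. The intent is not stated, and the restriction is worded as lung adenocarcinoma in Section 1.2 but as NSCLC in 2.1.2.1, which are not the same group. A line of confirmation would do no harm.

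The rest does not carry. The exception qualifies one inclusion route; it is not written as a general exclusion. Adjacent criteria, one excepting NSCLC and the other open to any malignancy, are at least as consistent with a deliberate choice as with an oversight. Moving the exception up to 2.1.2 would remove patients from the trial without evidence that the present rule is wrong. Reporting response with and without these patients is analysis detail that a SAP or the Master Protocol commonly holds, and neither is at hand.

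**Conclusion.** The observation is correct: on the subprotocol text alone, NSCLC with T790M plus a listed rare mutation is eligible, and the document does not remark on it. It is not a defect that calls for a change. The operative rule gives a single answer and agrees with the stated aims. The censoring note gives no ground for dropping such a patient later.

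No bias of known size or direction is shown. The illustrative shifts of 0 to 1.5 points per patient among 35 rest on an assumed 10% background rate and on a range of response rates whose upper end is borrowed from a largely different genotype. The number of such patients is not given and is probably small, since Section 1.2 itself calls the rare variants a small minority of EGFR mutations.

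This conclusion is limited to the protocol shown. Sections 2.1.1 and 2.1.2 defer to the Master Protocol for general eligibility and for determining the qualifying aberration, and that document may already say how a tumour with two actionable variants is assigned. Confirming the intent, citing the Master Protocol section that settles it, or aligning the lung terms in 1.2 and 2.1.2.1 would be optional tidying.

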3.2 Adverse Event Reporting Requirements

The Adverse Event Reporting Requirements for all EAY131 subprotocols are outlined in the MATCH MASTER protocol. Please refer to those guidelines when determining if an event qualifies as a Serious Adverse Event (SAE) and requires expedited reporting via CTEP's Adverse Event Reporting System (CTEP-AERS).

In addition, the following section outlines agent specific requirements and must be followed to ensure all reporting requirements are met.

3.2.1 Additional instructions, requirements and exceptions for protocol EAY131-E

Additional Instructions

For instructions on how to specifically report events that result in persistent or significant disability/incapacity, congenital anomaly, or birth defect events via CTEP-AERS, please contact the AEMD Help Desk at [contact] or [contact]. This will need to be discussed on a case-by-case basis.

Rev. Add25

EAY131-E specific expedited reporting requirements:

• **Pregnancies**: Pregnancies and suspected pregnancies (including a positive or inconclusive pregnancy test, regardless of age or disease state) occurring while the female patient is on osimertinib (AZD9291), or within 28 days of the female patient's last dose of osimertinib (AZD9291), are considered immediately reportable events. The pregnancy, suspected pregnancy, or positive/ inconclusive pregnancy test must be reported via CTEP-AERS within 24 hours of the Investigator's knowledge. Please refer to Appendix VIII in MATCH Master Protocol for detailed instructions on how to report the occurrence of a pregnancy as well as the outcome of all pregnancies.

EAY131-E specific expedited reporting exceptions:

For study Subprotocol E, the adverse events listed below do not require expedited reporting via CTEP-AERS:

- If an AE meets the reporting requirements of the protocol, and it is listed on the SPEER, it should ONLY be reported via CTEP-AERS if the grade being reported exceeds the grade listed in the parentheses next to the event.
- 3.2.2 Second Primary Cancer Reporting Requirements

All cases of second primary cancers, including acute myeloid leukemia (AML) and myelodysplastic syndrome (MDS), that occur following treatment on NCI-sponsored trials must be reported as follows.

- A second malignancy is a cancer that is UNRELATED to any prior anti-cancer treatment (including the treatment on this protocol). Second malignancies require ONLY routine reporting as follows:
 - 1. Complete a Second Primary Form in Medidata Rave within 14 days.
 - 2. Upload a copy of the pathology report to ECOG-ACRIN via Medidata Rave confirming the diagnosis.
 - 3. If the patient has been diagnosed with AML/MDS, upload a copy of the cytogenetics report (if available) to ECOG-ACRIN via Medidata Rave.
- A secondary malignancy is a cancer CAUSED BY any prior anticancer treatment (including the treatment on this protocol). Secondary malignancies require both routine and expedited reporting as follows:
 - 1. Complete a Second Primary Form in Medidata Rave within 14 days
 - 2. Report the diagnosis on the Adverse Event Form or Late Adverse Event Form in the appropriate Treatment Cycle or Post Registration folder in Medidata Rave

Report under a.) leukemia secondary to oncology chemotherapy, b.) myelodysplastic syndrome, or c.) treatment related secondary malignancy

- **NOTE:** When reporting attribution on the AE Form, assess the relationship between the secondary malignancy and the current protocol treatment ONLY (and NOT relationship to any anti-cancer treatment received either before or after protocol treatment).
- 3. Report the diagnosis via CTEP-AERS at http://ctep.cancer.gov
- 4. Upload a copy of the pathology report to ECOG-ACRIN via Medidata Rave and submit a copy to NCI/CTEP confirming the diagnosis.
- 5. If the patient has been diagnosed with AML/MDS, upload a copy of the cytogenetics report (if available) to ECOG-ACRIN via Medidata Rave and submit a copy to NCI/CTEP.

- **NOTE:** The Second Primary Form and the CTEP-AERS report should not be used to report recurrence or development of metastatic disease.
- **NOTE:** If a patient has been enrolled in more than one NCIsponsored study, the Second Primary Form must be submitted for the most recent trial. ECOG-ACRIN must be provided with a copy of the form and the associated pathology report and cytogenetics report (if available) even if ECOG-ACRIN was not the patient's most recent trial.
- **NOTE:** Once data regarding survival and remission status are no longer required by the protocol, no follow-up data should be submitted via CTEP-AERS or by the Second Primary Form.

	ECOG-ACRIN Cancer Research	Group	NCI	EAY131-E Version Date: July 16, 2021 Update Date: August 12, 2015
Rev. 7/16 Rev. Add12	3.3 C	omprehensive Adverse Ev simertinib (AZD9291) (osin	ents and Potential Risks I nertinib, NSC 781254)	List (CAEPR) for
Rev. Add14 Rev. Add23 Rev. Add25 Rev. Add27 Rev. Add29	Th sin ag co Re ita sp to ht lin Be	he Comprehensive Adverse ngle list of reported and/or gent using a uniform prese pomprehensive list, a subset eporting (SPEER), appears alicized text. This subset of becific exceptions to exped the 'CTEP, NCI Guidelines tp://ctep.cancer.gov/protoc hes.pdf for further clarificati elow is the CAEPR for Osin	e Events and Potential Ri potential adverse events ntation of events by body t, the Specific Protocol Ex s in a separate column an AEs (SPEER) is a list of ited reporting to NCI (exc s: Adverse Event Reporting colDevelopment/electronic on. Frequency is provided mertinib (AZD9291).	sks list (CAEPR) provides a (AE) associated with an system. In addition to the ceptions to Expedited ad is identified with bold and events that are protocol ept as noted below). Refer ng Requirements' applications/docs/aeguide d based on 1342 patients.
	N	OTE: If an AE meets th listed on the SPE the grade being r next to the event	e reporting requirements ER, it should ONLY be re eported exceeds the grad in the SPEER.	of the protocol, and it is eported via CTEP-AERS if le listed in the parentheses
	-		Vers	sion 2.7, October 19, 2020 ¹
	F	Adverse Events with Po Relationship to AZD9291 (os (CTCAE 5.0 Term) [n= 1342]	essible simertinib)	Specific Protocol Exceptions to Expedited Reporting (SPEER)
	Likely (>20%)	Less Likely (<=20%)	Rare but Serious (<3%)	
	BLOOD AND LYN	PHATIC SYSTEM DISORDE	RS	
		Anemia		Anemia (Gr 2)
	CARDIAC DISOR	DERS	1	
			Heart failure	
	EYE DISORDERS	5	1_	
			Dry eye Eye disorders - Other (thinning of the front layer of the eye)	
	CASTRONITECT		Neratitis	
	Diarrhea			Diarrhea (Gr. 2)
	Mucositis oral			Mucositis oral (Gr 2)
	WILCOSILIS OF AI	Nausea		
		Vomiting		
	INFECTIONS AND	DINFESTATIONS	ļ	
	Paronychia			Paronychia (Gr 2)
	INVESTIGATIONS	S	•	
		Creatinine increased		

	Adverse Events with Po Relationship to AZD9291 (or (CTCAE 5.0 Term) [n= 1342]	ssible simertinib)	Specific Protocol Exceptions to Expedited Reporting (SPEER)
Likely (>20%)	Less Likely (<=20%)	Rare but Serious (<3%)	
		Ejection fraction decreased	
	Electrocardiogram QT corrected interval prolonged		Electrocardiogram QT corrected interval prolonged (Gr 3)
	Lymphocyte count decreased		Lymphocyte count decreased (Gr 2)
	Neutrophil count decreased		Neutrophil count decreased (Gr 2)
	Platelet count decreased		Platelet count decreased (Gr 2)
	White blood cell decreased		White blood cell decreased (Gr 2)
METABOLISM AI	ND NUTRITION DISORDERS		(
	Anorexia		Anorexia (Gr 2)
RESPIRATORY,	THORACIC AND MEDIASTIN	IAL DISORDERS	
	Epistaxis		
	Respiratory, thoracic and mediastinal disorders - Other (interstitial lung disease) ²		Respiratory, thoracic and mediastinal disorders - Other (interstitial lung disease) ² (Gr 2)
		Pulmonary edema	
SKIN AND SUBC	UTANEOUS TISSUE DISORI	DERS	
	Alopecia		
Dry skin			Dry skin (Gr 2)
		Erythema multiforme	
	Nail changes ³		Nail changes ³ (Gr 2)
	Pruritus		Pruritus (Gr 2)
	Rash acneiform		Rash acneiform (Gr 2)
Rash maculo- papular			Rash maculo-papular (Gr 2)
	Skin and subcutaneous tissue disorders - Other (skin fissures)		
		Stevens-Johnson syndrome	

¹ This table will be updated as the toxicity profile of the agent is revised. Updates will be distributed to all Principal Investigators at the time of revision. The current version can be obtained by contacting

[contact]. Your name, the name of the investigator, the protocol and the agent should be included in the e-mail.

- ²Interstitial lung disease includes the terms pneumonitis and interstitial lung disease. Dyspnea, cough and fever may be indicative of interstitial lung disease/pneumonitis.
- ³Nail changes may include the terms nail bed disorders, nail discoloration, nail disorder, nail loss, nail pigmentation, nail toxicity, nail dystrophy, nail ridging, onychoclasis, onycholysis, and onychomadesis.

Adverse events reported on AZD9291 (osimertinib) trials, but for which there is insufficient evidence to suggest that there was a reasonable possibility that AZD9291 (osimertinib) caused the adverse event:

CARDIAC DISORDERS - Atrial fibrillation; Atrial flutter; Cardiac arrest; Myocardial infarction; Supraventricular tachycardia

EYE DISORDERS - Vision decreased

GASTROINTESTINAL DISORDERS - Constipation; Dry mouth; Dyspepsia; Dysphagia; Gastritis; Gastrointestinal disorders - Other (intestinal ischemia); Pancreatitis

GENERAL DISORDERS AND ADMINISTRATION SITE CONDITIONS - Death NOS; Fatigue; Fever²; Flu like symptoms; Generalized edema; Non-cardiac chest pain

INFECTIONS AND INFESTATIONS - Folliculitis; Lung infection; Nail infection; Papulopustular rash; Rash pustular; Shingles; Upper respiratory infection

INJURY, POISONING AND PROCEDURAL COMPLICATIONS - Other (drug eruption)

INVESTIGATIONS - Alanine aminotransferase increased; Aspartate aminotransferase increased; CPK increased; GGT increased; Investigations - Other (electrocardiogram QT interval abnormal); Weight loss

METABOLISM AND NUTRITION DISORDERS - Dehydration; Hyperglycemia; Hypermagnesemia; Hypokalemia; Hyponatremia

MUSCULOSKELETAL AND CONNECTIVE TISSUE DISORDERS - Back pain; Generalized muscle weakness; Neck pain

NERVOUS SYSTEM DISORDERS - Dizziness; Headache; Ischemia cerebrovascular; Stroke

RESPIRATORY, THORACIC AND MEDIASTINAL DISORDERS - Cough²; Dyspnea²; Hypoxia; Pleural effusion; Respiratory failure

SKIN AND SUBCUTANEOUS TISSUE DISORDERS - Eczema; Palmar-plantar erythrodysesthesia syndrome; Skin and subcutaneous tissue disorders - Other (skin erosion)

VASCULAR DISORDERS - Hematoma; Thromboembolic event

NOTE: AZD9291 (osimertinib) in combination with other agents could cause an exacerbation of any adverse event currently known to be caused by the other agent, or the combination may result in events never previously associated with either agent.

Rev. Add29 3.4 Dose Modifications

Rev. Add13

Rev. Add13

All toxicity grades below are described using the NCI Common Terminology Criteria for Adverse Events (CTCAE) version 4.0.

All appropriate treatment areas should have access to a copy of the CTCAE version 4.0. A copy of the CTCAE version 4.0 can be downloaded from the CTEP website (http://ctep.cancer.gov).

If there is a clinically-significant AE or unacceptable toxicity of any kind (grade 3 of greater), the primary treatment strategy should be dose interruption and supportive care aimed at the AE. The patient may resume osimertinib (AZD9291) dosing once the AE has resolved to grade 2 or less (see exceptions below). Dosing may resume at 80mg QD or 40mg QD at the discretion of the investigator provided the AE resolved to grade 2 or less within 21 days of dose interruption. If the toxicity does not resolve within 21 days to grade 2 or less, the patient should be removed from the protocol and followed until resolution.

Upon resolution of toxicity within 21 days and resumption of study drug:

- If a further episode of the same AE subsequently requires dose interruption, osimertinib (AZD9291) must restart at 40mg QD.
- If a different AE subsequently requires dose interruption, osimertinib (AZD9291) may restart at either 80mg QD or 40mg QD at the investigator's discretion

Adverse Events of Special Interest

1. Ophthalmic Events

Full ophthalmic assessment, including slit lamp examination, is required if a patient experiences any visual symptoms (including blurring of vision) (grade 2 or greater), with additional tests if clinically indicated. Any clinically significant findings, including those confirmed by the ophthalmologist must be reported as an event on the eCRF in Medidata Rave. Ophthalmology examination results should be collected in the eCRF in Medidata Rave. Patient will be advised to consult the clinic promptly if they have any concerns.

Keratitis

Keratitis was reported in 0.7% (n=6) of the 833 patients treated with osimertinib in the AURA studies. Patients presenting with signs and symptoms suggestive of keratitis such as acute or worsening: eye inflammation, lacrimation, light sensitivity, blurred vision, eye pain and/or red eye should be referred promptly to an ophthalmology specialist.

2. Interstitial lung disease

If new or worsening pulmonary symptoms (eg, dyspnea) or radiological abnormality suggestive of interstitial lung disease is observed, an interruption in study treatment dosing is required as well as a full diagnostic workup to exclude alternative causes such as lymphangitic carcinomatosis, infection, allergy, cardiogenic edema, or pulmonary hemorrhage. In the presence of confirmatory High Resolution CT scans where other causes of respiratory symptoms have been excluded, a diagnosis of interstitial lung disease should

16

be considered and study treatment permanently discontinued. In the absence of a diagnosis of interstitial lung disease study treatment may be restarted following consultation with the study subprotocol Pl's.

Rev.2/16 Rev. Add13 3. Cardiovascular effects

Exclusion criteria for unstable cardiac conditions and risk factors for QT prolongations are included in the clinical study protocol. Concomitant use of regular medications that may prolong the QT interval will be restricted whenever feasible, but patients may receive any medication that is clinically indicated for the treatment of AEs. Electrolyte and vital sign assessments, including pulse rate and blood pressure, will be monitored regularly throughout the study. ECG will be performed at enrollment and prior to each treatment cycle. The investigator or designated physician will review each ECG prior to discharge from the clinic and may refer to a local cardiologist if appropriate for immediate management of the patient. A paper copy should be filed in the patient's medical records. If an abnormal ECG finding at screening or baseline is considered to be clinically significant by the investigator, it should be reported as a concurrent condition.

QTc Prolongation

Patients with QTcF prolongation fulfilling the following criteria (i.e., confirmed QTcF prolongation to > 500 msec absolute or a > 60 msec increase from baseline) should have osimertinib (AZD9291) interrupted and regular ECGs performed until resolution to baseline. If the toxicity does not resolve to < grade 1 within 3 weeks the patient will be permanently withdrawn from osimertinib (AZD9291) treatment.

Changes in Cardiac Contractility

Across clinical trials, Left Ventricular Ejection Fraction (LVEF) decreases greater than or equal to 10% and a drop to less than 50% occurred in 4.0% (26/655) of patients treated with osimertinib who had baseline and at least one follow-up LVEF assessment. Based on the available clinical trial data, a causal relationship between effects on changes in cardiac contractility and osimertinib has not been established. In patients with cardiac risk factors and those with conditions that can affect LVEF, cardiac monitoring, including an assessment of LVEF at baseline and during treatment, should be considered. In patients who develop relevant cardiac signs/symptoms during treatment, cardiac monitoring including LVEF assessment should be considered.

3.5 Supportive Care

All supportive measures consistent with optimal patient care will be given throughout the study.

